Protocol		Date:	23 November 2015	Novo Nordisk
Study ID: NN8022-4241		Version:	5.0	
UTN: U1111-1185-3661		Status:	Final	
FILPAS No:	CONFIDENTIAL	Page.	1 of 53	

Protocol

Study ID: NN8022-4241

In-market utilisation of liraglutide used for weight management in Europe: a retrospective medical record review study

Redacted protocol Includes redaction of personal identifiable information only.

Non-interventional study

(1) Novo Nordisk – Epidemiology;	

Protocol originator:-

This confidential document is the property of Novo Nordisk. No unpublished information contained herein may be disclosed without prior written approval from Novo Nordisk. Access to this document must be restricted to relevant parties.

Protocol		Date:	23 November 2015	Novo Nordisk
Study ID: NN8022-4241		Version:	5.0	
UTN: U1111-1185-3661		Status:	Final	
EU PAS No.:	CONFIDENTIAL	Page:	2 of 53	

PASS information

1 ASS IIIUI IIIatiuii	
Title	In-market utilisation of liraglutide used for weight management in Europe: a retrospective medical record review study
Protocol version identifier	5.0
Date of last version of protocol	23 November 2015
EU PAS Register number	Study to be registered
Active substance	Liraglutide (ATC code: A10BX07)
Medicinal product	Saxenda [®] Victoza [®]
Product reference	
Procedure number	
Marketing authorisation holder(s)	Novo Nordisk
Joint Post Authorisation Safety Study (PASS)	No
Research question and objectives	To investigate in-market utilisation of liraglutide used for weight management: • Use of Saxenda® according to approved indication. • Use of Victoza® for weight management. • Use of Saxenda® according to approved posology.
Country(-ies) of study	Two European Union (EU) countries
Author	

Marketing authorisation holder(s)

Marketing authorisation holder (s) (MAH (s))	Novo Nordisk [name]
MAH contact person	

CONFIDENTIAL

23 November 2015 | Novo Nordisk Date: 5.0 Final Version: Status: 3 of 53 Page:

Table of Contents

				Page
Ma	arketin	g authoris	sation holder(s)	2
Ta	ble of (Contents		3
1	List o	of abbrevia	ations	5
2			rties	
	•	-		
3				
	3.1		11111	
	3.2 3.3		le and background	
	3.3 3.4		th question and objectives	
	3.4	-	esign	
	3.6		iones	
	3.7		ize	
	3.8	•	alysis	
			, and the second	
4			nd updates	
5	Miles	tones		14
6	Ratio	nale and b	background	14
7	Resea	arch quest	ion and objectives	15
	7.1	Primary	objective	15
	7.2	Seconda	ary objective(s)	16
	7.3	Endpoir	nts	16
8	Resea	arch meth	ods	18
	8.1	Study d	esign	18

3.2 Rationale and background

As part of the risk management plan (RMP) for Saxenda[®], the aim of this study is to investigate usage of liraglutide for weight management in clinical practice.

3.3 Research question and objectives

The aim of this study is to investigate in-market utilisation of liraglutide used for weight management. Specifically, the primary and secondary objectives are to investigate the following:

Primary objective:

To assess the use of Saxenda® according to the approved indication:

Saxenda is indicated as an adjunct to a reduced-calorie diet and increased physical activity for weight management in adult patients with an initial Body Mass Index (BMI) of

- $\geq 30 \text{ kg/m}^2$ (obese), or
- \geq 27 kg/m² to \leq 30 kg/m² (overweight) in the presence of at least one weight-related comorbidity such as dysglycaemia (pre-diabetes or type 2 diabetes mellitus), hypertension, dyslipidaemia or obstructive sleep apnoea.

Treatment with Saxenda should be discontinued after 12 weeks on the 3.0 mg/day dose if patients have not lost at least 5% of their initial body weight.

The following endpoints will address the primary objective:

BMI and comorbidities:

• Number of patients with BMI\ge 30 kg/m² (measured less than 6 months before date of first prescription).

Protocol		Date:	23 November 2015	Novo Nordisk
Study ID: NN8022-4241		Version:	5.0	
UTN: U1111-1185-3661		Status:	Final	
EU PAS No.:	CONFIDENTIAL	Page:	9 of 53	

- Number of patients with 27 kg/m² ≤BMI < 30 kg/m² (measured less than 6 months before date of first prescription) and
 - ≥1 relevant comorbidity registered:
 - Dysglycaemia (Type 2 Diabetes Mellitus [T2DM] or prediabetes), hypertension, dyslipidaemia, and/or obstructive sleep apnoea.
 - o No relevant comorbidities (described above) registered.
- Number of patients with BMI<27 kg/m² (measured less than 6 months before date of first prescription).
- Number of patients with BMI not measured within 6 months before date of first prescription.

Stopping rule:

- Number of patients with at least 5% weight loss (measured 16-24 weeks after first prescription date) and continuing treatment.
- Number of patients with less than 5% weight loss (measured 16-24 weeks after first prescription date) and continuing treatment.
- Mean weight loss (measured 16-24 weeks after first prescription date) in patients not treated according to stopping rule.

Secondary objectives:

- 1. To assess the use of Victoza® for weight management.
- 2. To assess the use of Saxenda® according to the approved posology.

The following endpoint will be used to address the first secondary objective:

- Number of patients with Victoza[®] prescriptions fulfilling at least one of the following criteria:
 - o Dose information of 3.0 mg per day, or
 - o Indication of weight management.

Protocol		Date:	23 November 2015	Novo Nordisk
Study ID: NN8022-4241		Version:	5.0	
UTN: U1111-1185-3661		Status:	Final	
EU PAS No ·	CONFIDENTIAL	Page.	10 of 53	

The following endpoints will be used to address the second secondary objective:

- Adherence to dose escalation according to label:
 - Number of patients who have reached a dose of 3.0 mg within 4-12 weeks after first prescription date.
- Concomitant medication with other GLP-1 receptor agonists:
 - Number of Saxenda[®] patients with other GLP-1 receptor agonists prescribed during continued treatment with Saxenda[®] (continued treatment is defined as no gaps between prescriptions of more than 90 days, identified by examining repeat prescription dates).
- Duration of treatment with Saxenda[®]:
 - o Number of patients with a treatment duration of:
 - 0-6, 7-12, 13-18, or 19-24 months, or ongoing (current patients), with continued treatment defined as no gaps between prescriptions of more than 90 days, identified by examining repeat prescription dates.

3.4 Study design

This drug utilisation study (DUS) is a non-interventional, multi-centre post-authorisation safety study (PASS) to investigate the use of Saxenda[®] and Victoza[®] in clinical practice in patients who have initiated either treatment in the Saxenda[®] postmarketing period. The DUS involves retrospective review of patients' medical records in two selected European Union (EU) countries, 24 months after launch of Saxenda[®] in each of the countries. Physician sites will be selected using several tools, including intelligence databases, e.g., IMS LifeLinkTM, to obtain a representative sample of prescriptions. A pilot study, which is embedded in the full study, will be conducted 6 months after launch of Saxenda[®] in each of the two countries, prior to the full DUS. Patients will be treated according to routine clinical practice at the discretion of the treating physician. The study will gather data over the course of routine treatment for Saxenda[®] and Victoza[®] treated patients.

3.5 Population

Inclusion criteria:

To be eligible for the study, patients will be required to meet both of the following inclusion criteria:

Protocol		Date:	23 November 2015	Novo Nordisk
Study ID: NN8022-4241		Version:	5.0	
UTN: U1111-1185-3661		Status:	Final	
EU PAS No.:	CONFIDENTIAL	Page:	11 of 53	

- 1. Initiation of Saxenda[®] or Victoza[®] (initiation is defined as no prescription of the same brand within the previous 12 months).
- 2. Informed consent obtained before any study-related activities. Study-related activities are any procedures that are carried out as part of the study, including activities to determine suitability of the study.

Exclusion criteria:

The following exclusion criteria will be applied:

- 1. Patients or physicians who previously participated in interventional studies for Saxenda® or Victoza® will not be eligible to participate in the study.
- 2. For the full study, sites and patients included in the pilot will be excluded.

Withdrawal criteria:

The patient may withdraw at will at any time.

3.6 Variables

- **Site characteristics:** geographic location, specialty or area of primary practice, practice type, practice size and patient volume.
- Patient demographics, medical history and other characteristics: date of birth, sex, and for Saxenda® patients also body weight and height (and date of anthropometric measurements).

• Drug utilisation:

- Saxenda[®] or Victoza[®] patients: brand name, indication prescribed at first prescription, target dose prescribed at first prescription, repeat prescription dates
- Saxenda[®] patients only: treatment start and end dates, comorbidities (dysglycaemia i.e. T2DM or prediabetes; hypertension, dyslipidaemia, and/or obstructive sleep apnoea), concomitant medication with other glucagon-like peptide-1 (GLP-1) receptor agonist, dose at 4-12 weeks and 16-24 weeks post initiation of treatment, body weight at 16-24 weeks post initiation of treatment.
- o Victoza® patients only: dose throughout the treatment period.

Protocol		Date:	23 November 2015	Novo Nordisk
Study ID: NN8022-4241		Version:	5.0	
UTN: U1111-1185-3661		Status:	Final	
EU PAS No.:	CONFIDENTIAL	Page:	12 of 53	

3.7 Study size

This is a descriptive study designed to examine in-market utilisation of liraglutide; thus there will be no hypothesis testing and a power calculation is not applicable. 100 patients will be enrolled for the pilot study (50 in each country, with 25 patients using Saxenda® and 25 patients using Victoza®) and additionally 300 patients will be enrolled for the full study (150 in each country, with 75 patients using Saxenda® and 75 patients using Victoza®).

3.8 Data analysis

This is a descriptive study that will investigate in-market utilisation of liraglutide. No formal statistical testing will be carried out.

Protocol		Date:	23 November 2015	Novo Nordisk
Study ID: NN8022-4241		Version:	5.0	
UTN: U1111-1185-3661		Status:	Final	
FILPAS No.	CONFIDENTIAL	Page.	13 of 53	

4 Amendments and updates

Amendment or update no	Date	Section of study protocol	Amendment or update	Reason

 Protocol
 Date:
 23 November 2015
 Novo Nordisk

 Study ID: NN8022-4241
 Version:
 5.0

 UTN: U1111-1185-3661
 Status:
 Final

Page:

14 of 53

5 Milestones

EU PAS No.:

Milestone	Planned date
Registration in the EU PAS Register	Q4 2016
Start of data collection (pilot)	November 2016
End of data collection (pilot)	August 2017
Pilot study report	November 2017
Start of data collection (full study)	April 2018
End of data collection (full study)	February 2019
Database lock	March 2019
End (or completion) of study	June 2019
Final report of study results	August 2019

This study will be registered prior to first data capture according to Novo Nordisk requirement on non-interventional study disclosure. Only the main study site per country will be disclosed via facility name, city and country on the study registration.

For PASS studies in Europe, the study information should be available in the EU Electronic Register of Post-Authorisation Studies (EU PAS Register) maintained by the European Medicines Agency and accessible through the European medicines web portal.

Note: Study registration is regarded as the publication of an internationally-agreed set of information (which can be found at the World Health Organisation [WHO] homepage) about the design, conduct and administration of clinical trials. These details are published on a publicly-accessible website managed by a registry conforming to WHO standards (also found at the WHO homepage), eg www.clinicaltrials.gov.

6 Rationale and background

Saxenda[®] and Victoza[®] are both medicinal products containing the active substance liraglutide. Liraglutide is a long-acting glucagon-like peptide-1 (GLP-1) analogue (incretin mimetic), which has

Protocol		Date:	23 November 2015	Novo Nordisk
Study ID: NN8022-4241		Version:	5.0	
UTN: U1111-1185-3661		Status:	Final	
EU PAS No.:	CONFIDENTIAL	Page:	15 of 53	

been shown to reduce hyperglycaemia in patients with type 2 diabetes mellitus (T2DM). The mechanisms of action for liraglutide include stimulation of insulin secretion and decrease of glucagon secretion, both in a physiological and glucose dependent-manner. The effects of liraglutide also include reduced sensation of hunger and increased satiety, leading to decreased food intake and subsequent weight loss.

Victoza[®] is indicated for the treatment of adults with T2DM at doses of 1.2 mg and 1.8 mg, and received marketing authorisation from the European Medicines Agency (EMA) in June 2009. Saxenda[®] (liraglutide 3.0 mg) is indicated as an adjunct to a reduced-calorie diet and increased physical activity for weight management in adults who are obese, or adults who are overweight with at least one weight-related comorbidity. The efficacy of Saxenda[®] was demonstrated in five phase 2 and 3 clinical trials involving around 5,800 obese/overweight patients, which showed that more patients administered Saxenda[®] achieved clinically relevant weight loss than those treated with placebo. Saxenda[®] received marketing authorisation from the EMA in March 2015.

As defined in the Risk Management Plan (RMP) for Saxenda[®], a retrospective drug utilisation study (DUS) to investigate patterns of use of Saxenda[®] and Victoza[®] in routine clinical practice has been requested by the EMA as a post marketing requirement. As is the case with any medicinal product, real-world use of Saxenda[®] or Victoza[®] may differ from the approved indication or recommendations outlined in the Summary of Product Characteristics (SmPC) (1, 2). Considering that these two liraglutide products with the same strength and formulation will be available for different indications with different doses, there is the potential for inadvertent use of one or the other product for either indication. The DUS will allow assessment of usage patterns of liraglutide for weight management, and thereby could refine pharmacovigilance planning and risk management.

7 Research question and objectives

The aim of this study is to investigate in-market utilisation of liraglutide for weight management. Specifically, the primary and secondary objectives are the following:

7.1 Primary objective

To assess the use of Saxenda® according to the approved indication:

Saxenda is indicated as an adjunct to a reduced-calorie diet and increased physical activity for weight management in adult patients with an initial Body Mass Index (BMI) of

• $\geq 30 \text{ kg/m}^2 \text{ (obese), or}$

Protocol		Date:	23 November 2015	Novo Nordisk
Study ID: NN8022-4241		Version:	5.0	
UTN: U1111-1185-3661		Status:	Final	
EU PAS No.:	CONFIDENTIAL	Page:	16 of 53	

• ≥ 27 kg/m² to < 30 kg/m² (overweight) in the presence of at least one weight-related comorbidity such as dysglycaemia (pre-diabetes or type 2 diabetes mellitus), hypertension, dyslipidaemia or obstructive sleep apnoea.

Treatment with Saxenda should be discontinued after 12 weeks on the 3.0 mg/day dose if patients have not lost at least 5% of their initial body weight.

7.2 Secondary objective(s)

- 1. To assess the use of Victoza® for weight management.
- 2. To assess the use of Saxenda® according to the approved posology.

7.3 Endpoints

Primary endpoint:

The following endpoints will address the primary objective (concerning Saxenda® only):

BMI and comorbidities:

- Number of patients with Body Mass Index (BMI)≥30 kg/m² (measured less than 6 months before date of first prescription).
- Number of patients with 27 kg/m² ≤BMI<30 kg/m² (measured less than 6 months before date of first prescription) and
 - ≥1 relevant comorbidity registered:
 - Dysglycaemia (T2DM or prediabetes), hypertension, dyslipidaemia, and/or obstructive sleep apnoea.
 - o No relevant comorbidities (described above) registered.
- Number of patients with BMI<27 kg/m² (measured less than 6 months before date of first prescription).
- Number of patients with BMI not measured within 6 months before date of first prescription.

 Protocol
 Date:
 23 November 2015
 Novo Nordisk

 Study ID: NN8022-4241
 Version:
 5.0

 UTN: U1111-1185-3661
 Status:
 Final

 EU PAS No.:
 CONFIDENTIAL
 Page:
 17 of 53

Stopping rule:

- Number of patients with at least 5% weight loss (measured 16-24 weeks after first prescription date) and continuing treatment.
- Number of patients with less than 5% weight loss (measured 16-24 weeks after first prescription date) and continuing treatment.
- Mean weight loss (measured 16-24 weeks after first prescription date) in patients not treated according to stopping rule.

Secondary endpoint:

The following endpoint will be used to address the first secondary objective (concerning Victoza[®] only):

- Number of patients with Victoza[®] prescriptions fulfilling at least one of the following criteria:
 - 1. Dose information of 3.0 mg per day, or
 - 2. Indication of weight management.

The following endpoints will be used to address the second secondary objective (concerning Saxenda® only):

- Adherence to dose escalation according to label:
 - o Number of patients who have reached a dose of 3.0 mg within 4-12 weeks after first prescription date.
- Concomitant medication with of other GLP-1 receptor agonists:
 - Number of Saxenda[®] patients with other GLP-1 receptor agonists prescribed during continued treatment with Saxenda[®] (continued treatment is defined as no gaps between prescriptions of more than 90 days, identified by examining repeat prescription dates).
- Duration of treatment with Saxenda®:
 - o Number of patients with a treatment duration of:

Protocol		Date:	23 November 2015	Novo Nordisk
Study ID: NN8022-4241		Version:	5.0	
UTN: U1111-1185-3661		Status:	Final	
EU PAS No.:	CONFIDENTIAL	Page:	18 of 53	

• 0-6, 7-12, 13-18, or 19-24 months, or ongoing (current patients), with continued treatment defined as no gaps between prescriptions of more than 90 days, identified by examining repeat prescription dates.

8 Research methods

In this document physician refers to the individual overall responsible for the conduct of the non-interventional study at a study site.

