8.1.3 Treatment of patients

Patients will be treated with commercially available Saxenda® or Victoza® according to routine clinical practice at the discretion of the treating physician. Saxenda® and Victoza® both contain the

Protocol		Date:	23 November 2015	Novo Nordisk
Study ID: NN8022-4241		Version:	5.0	
UTN: U1111-1185-3661		Status:	Final	
FILPAS No.	CONFIDENTIAL	Page.	21 of 53	

active substance liraglutide - a long-acting GLP-1 analogue, and are both administered subcutaneously by injection. The approved posology for Saxenda[®] is a starting dose of 0.6 mg daily, which should be increased to 3.0 mg daily in increments of 0.6 mg with at least one week intervals to improve gastrointestinal tolerability. For Victoza[®], the approved posology is a starting dose of 0.6 mg daily, which should be increased to 1.2 mg after at least one week; based on glycaemic response, the daily dose can be increased from 1.2 mg to 1.8 mg after at least one week.

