8.2.6 Flowchart

The data collection period for Saxenda[®]/Victoza[®] will be the interval between the launch date of Saxenda[®] to the index date of the pilot or full study, respectively. Table 1 and Table 2 show the data to be collected respectively for Saxenda[®] and Victoza[®] patients at different time points in relation to initiation of treatment. Data collection will encompass the following treatment periods for Saxenda[®]: (1) a time frame of 6 months prior to treatment initiation, (2) treatment initiation, (3) 4-12 weeks post treatment initiation, (4) 16-24 weeks post treatment initiation, and also (5) throughout the entire treatment period. Data collection will encompass the following treatment periods for Victoza[®]: (1) treatment initiation, and (2) throughout the entire treatment period.

Protocol	UTN: U1111-1185-3661	Date:	23 November 2015	Status:	Final	Novo Nordisk
Study ID: NN8022-4241	EU PAS No.:	Version:	5.0	Page:	23 of 53	

Table 1 - Saxenda® patients¹

Weeks in relation to initiation of treatment/time of first prescription	Prior to treatment initiation	0	4 – 12 weeks	16 – 24 weeks	Throughout the treatment period ²
Visit window			+4 weeks	+4 weeks	
Demography ³		X			
Co-morbidities ⁴	X				
Body Weight		X^5		X^6	
Adult height	X				
BMI		X^5			
Brand name		X			
Indication prescribed		X			
Target dose prescribed		X			
Current dose ⁷			X	X	
Treatment start date		X			
Treatment stop date					X
Concomitant medication with GLP-1					
receptor agonists					X
(Brand name and start date)					

- 1) Inclusion criteria must be fulfilled (incl. obtained informed consent) before data extraction is performed
- 2) Censoring at 24 months after launch
- 3) Sex, age
- 4) Diagnosis of or treatment of pre-diabetes, type 2 diabetes mellitus (T2DM), hypertension, dyslipidaemia and/or obstructive sleep apnoea.
- 5) Latest recording within 6 months before first prescription of Saxenda®
- 6) If not available the earliest subsequent body weight and date of measurement should be recorded
- 7) If treatment discontinuation occurs prior to/between the specified time points, the dose of Saxenda® at time of treatment discontinuation should be recorded.

Protocol		Date:	23 November 2015	Novo Nordisk
Study ID: NN8022-4241		Version:	5.0	
UTN: U1111-1185-3661		Status:	Final	
EU PAS No.:	CONFIDENTIAL	Page:	24 of 53	

Table 2 - Victoza® patients¹

Weeks in relation to initiation of treatment/time of first prescription	0	Throughout the treatment period ²

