8.3 Variables

Site characteristics:

To evaluate the representativeness of sites the following information will be collected for each participating site using a site questionnaire:

- Geographic location of physician site
- Specialty of participating physician (e.g., GPs, cardiologists, endocrinologists [or other diabetes and obesity specialists])
- Practice type (e.g., community hospital, academic/medical centre, office based)
- Practice size (number of physicians who practice at site)
- Patient volume (i.e., number of patients and estimated number of patients prescribed Saxenda[®] or Victoza[®]).

Additionally, the number of sites invited to participate within each specialty will be collected along with reason for refusal in order to evaluate the response rate and representativeness of the specialty. Sites and physicians will not be identifiable in the study report.

Patient demographics, medical history, and other characteristics:

- Date of birth
- Sex

Body weight (latest recording within 6 months before date of first prescription of Saxenda[®]), height, BMI (calculated), and date of anthropometric measurements (for Saxenda[®] patients only)

²⁾ Censoring at 24 months after launch

³⁾ Sex, age

 Protocol
 Date:
 23 November 2015
 Novo Nordisk

 Study ID: NN8022-4241
 Version:
 5.0

 UTN: U1111-1185-3661
 Status:
 Final

 EU PAS No.:
 CONFIDENTIAL
 Page:
 25 of 53

Drug utilisation:

Saxenda[®] or Victoza[®] patients:

- Brand name
- Indication prescribed at treatment initiation
- Target dose prescribed at treatment initiation
- Repeat prescription dates

Saxenda® patients only:

- Treatment start date and end date
- Comorbidities:
 - Dysglycaemia (T2DM or prediabetes), hypertension, dyslipidaemia, and/or obstructive sleep apnoea, before first prescription date. Diagnosis of dysglycaemia or dyslipidaemia may be based on relevant concomitant glucose lowering therapy (ATC code A10) or lipid lowering therapy (ATC code C10), respectively. In addition, diagnosis of dysglycaemia may be in the form of a relevant glycated haemoglobin (HbA1c), Oral Glucose Tolerance Test (OGTT) or fasting plasma glucose (FPG) measurement. According to the American Diabetes Association (ADA), prediabetes and diabetes may be defined based on the following laboratory cut-off values (4):

Prediabetes:

- FPG > 100 mg/dL (5.6 mmol/L) and < 125 mg/dL (6.9 mmol/L) and/or
- 2 hour post-challenge (OGTT) plasma glucose ≥ 140 mg/dL (7.8 mmol/L) and ≤ 199 mg/dL (11.0 mmol/L) and/or

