- HbA1c 5.7-6.4% (both inclusive)

T2DM:

- FPG \geq 126 mg/dL (7.0 mmol/L) and/or
- 2 hour post-challenge (during an OGTT) plasma glucose ≥ 200 mg/dL (11.1 mmol/L) and/or
- HbA1c > 6.5%
- O Diagnosis of obstructive sleep apnoea may be based on treatment with continuous positive airway pressure (CPAP) device.
- Concomitant medication with other GLP-1 receptor agonists (brand name and start date).
- Dose at 4-12 weeks and 16-24 weeks post initiation of treatment
- Body weight at 16-24 weeks post initiation of treatment. If body weight is not available within this interval, the earliest subsequent body weight and date of measurement should be recorded

Victoza® initators only:

• Dose throughout the treatment period

 Protocol
 Date:
 23 November 2015
 Novo Nordisk

 Study ID: NN8022-4241
 Version:
 5.0

 UTN: U1111-1185-3661
 Status:
 Final

 EU PAS No.:
 Page:
 26 of 53

Prescription outside label

Prescription outside label will be categorised as follows:

Saxenda® patients:

- BMI<27 kg/m² within 6 months before date of first prescription
- 27 kg/m² ≤BMI < 30 kg/m² within 6 months before date of first prescription and no relevant comorbidities registered (dysglycaemia [T2DM or prediabetes], hypertension, dyslipidaemia, and/or obstructive sleep apnoea)
- BMI not measured within 6 months before date of first prescription
- Non-adherence to dose escalation according to SmPC (i.e., daily dose of 3.0 mg not reached within 4-12 weeks post initiation of treatment)
- Non-adherence to stopping rule (i.e., less than 5% weight loss after 16-24 weeks on Saxenda[®] 3.0 mg and still on continued treatment)
- Concomitant medication with other GLP-1 receptor agonists

Victoza® patients:

- Dose of 3.0 mg per day
- Prescribed indication of weight management

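### The stopping-rule endpoint is timed from first prescription, not from each patient's time on 3.0 mg, and the listed Saxenda data do not give the date 3.0 mg was reached

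*Protocol*

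**What the plan says.** Protocol 7.1 gives the label rule: Saxenda "should be discontinued after 12 weeks on the 3.0 mg/day dose if patients have not lost at least 5" percent of starting weight. The endpoint meant to assess it, in 7.3 and repeated in 3.3 and 8.7.3, is the "Number of patients with less than 5% weight loss (measured 16-24 weeks after first prescription date) and continuing treatment". Its companions are the matching count with at least 5% loss, and the mean weight loss in patients not treated according to the rule.

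On escalation, 8.1.3 says the dose "should be increased to 3.0 mg daily in increments of 0.6 mg with at least one week intervals" from a start of 0.6 mg. Section 7.3 counts as adherent the "Number of patients who have reached a dose of 3.0 mg within 4-12 weeks after first prescription date".

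The data listed in 8.3 that bear on dose over time in Saxenda patients are:
- "Dose at 4-12 weeks and 16-24 weeks post initiation of treatment";
- "Target dose prescribed at treatment initiation";
- "Repeat prescription dates", with no dose attached;
- treatment start and end dates.

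Table 1 in 8.2.6 adds the dose at discontinuation if treatment stops early (note 7). For the 16-24 week weight, note 6 says: "If not available the earliest subsequent body weight and date of measurement should be recorded".

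The outside-label lists in 8.3 and 8.7.2 define the same failure in other words: under 5% loss following 16 to 24 weeks on Saxenda 3.0 mg, with treatment still continuing.

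**The concern.** The label's clock starts when the patient reaches 3.0 mg. The endpoint's clock starts at first prescription. The two agree only for a patient whose escalation time and weighing date happen to line up, so one cell of the table can mix patients who broke the rule with patients to whom it did not yet apply.

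This matters because the stopping rule is part of the primary objective, and non-adherence to it is one of the forms of outside-label prescribing that 8.7.2 makes the main analysis. The mean weight loss among patients not treated according to the rule inherits the same misclassification. Section 6 says the EMA requested the study as a post-marketing requirement, so this figure is one that the regulator will read.

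**Working it through.** **Inputs.** Start at 0.6 mg, steps of 0.6 mg at least one week apart (8.1.3). Accepted escalation 4-12 weeks and weighing window 16-24 weeks, both from first prescription (7.3). Label decision after 12 weeks on 3.0 mg (7.1). Saxenda patients in the full study: 150, or 75 per country (8.2.1).

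**The plan's own window.** Steps needed: (3.0 − 0.6)/0.6 = 4, so 3.0 mg is reached at week 4 at the earliest. Adding 12 weeks to the accepted range gives 4 + 12 = 16 and 12 + 12 = 24. The protocol does not state this derivation, but it reproduces the window exactly.

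**The same window per patient.** Let r be the week 3.0 mg is reached and w the week of weighing. Time on 3.0 mg is T = w − r, and the label decision falls at week r + 12. The part of the window before that point is (r + 12 − 16)/8 = (r − 4)/8.

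| r | Decision week | T at w = 16 | T at w = 20 | T at w = 24 | Window before decision |
|---|---|---|---|---|---|
| 4 | 16 | 12 | 16 | 20 | 0% |
| 6 | 18 | 10 | 14 | 18 | 25% |
| 8 | 20 | 8 | 12 | 16 | 50% |
| 10 | 22 | 6 | 10 | 14 | 75% |
| 12 | 24 | 4 | 8 | 12 | 100% |

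So T runs from 16 − 12 = 4 to 24 − 4 = 20 weeks. If Table 1's +4 weeks applied to both dose and weight, the range would be 16 − 16 = 0 to 28 − 4 = 24.

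**Errors in both directions.**
- r = 12, weighed at week 16 with under 5% loss and continuing: 4 weeks on 3.0 mg, within label, but counted with the rule-breakers.
- r = 4, under 5% at week 16, continues, weighed at week 24 with 5% or more: 24 − 16 = 8 weeks past the decision point, and counted as compliant.

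**What the listed data can settle.** A patient not on 3.0 mg at weeks 16-24 can be set aside. For the rest, if all that is known is r between 4 and 12, T lies between w − 12 and w − 4: 4-12 weeks at w = 16, 8-16 at w = 20, 12-20 at w = 24. Twelve weeks on dose is certain only from week 24, the last point of the window. A target dose named at initiation does not show when it was reached, and repeat prescription dates without doses do not either.

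**The other wording (8.3, 8.7.2).** If 3.0 mg there means the dose, assessment falls between weeks 4 + 16 = 20 and 12 + 24 = 36, after 16 to 24 weeks on dose instead of 12, and needs the date that is not listed. If it only names the product, which section 6 describes as liraglutide 3.0 mg, the timing problem is that of 7.3.

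**Illustration of scale (assumed, not in the documents).** With weighing uniform over weeks 16-24 and r uniform on 4 to b, the share weighed too early is (b − 4)/16: 0% if all reach 3.0 mg at week 4, 12.5% for b = 6, 25% for b = 8, 50% for b = 12. Only those who also have under 5% loss and continue are wrongly counted as non-adherent. One misclassified patient shifts the full-study proportion by at least 1/150 = 0.67 points, or 1/75 = 1.33 points in one country.

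**The case against.** The window is a sensible proxy. It equals escalation plus 12 weeks, and under the fastest labelled escalation no weight inside it is too early. Section 8.9 admits that routine records do not follow fixed assessment times, 8.7.3 warns that stopping-rule data will be limited in the pilot, and 8.1.1 uses the pilot to test variable availability and allows refinement. The 4-week case pairs the slowest accepted escalation with the earliest weight, and no endpoint text uses the +4 weeks. The choice among several weights inside the window is an ordinary matter for the analysis plan. All of this stands, and it limits how much weight the point can bear. It does not supply the missing anchor: an analysis plan cannot use a date that was never abstracted.

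A reader might infer that non-adherence is overstated. The documents do not support this. Fast escalators weighed late pull the other way, as do the post-window weights that note 6 accepts. And if the wording in 8.3 and 8.7.2 refers to the dose, everyone counted in the main analysis has had at least 16 weeks on 3.0 mg, so no one still inside the 12 weeks is included.

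A reader might also infer from note 6 that any early weight shuts out a better one. The note only stops the search for weights after the window. A week-17 weight does not exclude a week-23 weight.

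**Conclusion.** The point holds as one of misclassification with unknown net direction. The endpoint does not measure the label rule patient by patient: time on 3.0 mg at weighing ranges from 4 to 20 weeks against the label's 12, for patients who escalate within the accepted 4-12 weeks. The listed data resolve this only in part, and two sections use a definition that matches neither the label nor, if it means the dose, 7.3. How many patients are affected cannot be derived from the documents, because it depends on escalation speed, weighing dates, weight loss and continuation together. The shares above rest on assumed uniform distributions, and the points per patient show scale only; they do not estimate an effect. This should be corrected before full-study abstraction begins, but it does not undermine the study as a whole.

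**What to change.** Add to the Saxenda CRF the recorded date of the step to 3.0 mg daily, as distinct from the date on which 3.0 mg was named as the target. Record the first weight at or after 12 weeks from that date, up to a stated limit (for example 20 weeks on 3.0 mg, which is week 32 for a patient reaching it at week 12), in place of the note 6 rule for this endpoint. Use this one definition in 3.3, 7.3, 8.3, 8.7.2 and 8.7.3. Report as separate not-assessable groups the patients who never reached 3.0 mg, those without the date, and those censored before 12 weeks on 3.0 mg. Keep the week 16-24 weight and its count, for all patients, as a supportive result.

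The cost is one more abstracted date, a re-anchored weight and aligned wording in five sections. The date will sometimes be missing, so the assessable denominator shrinks. If better-documented patients are also better managed, the assessable group may look more adherent than the whole; the retained week 16-24 count helps to show this. Some spread in late weighing remains, up to the stated limit.

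Censoring at the index date also bites. The latest start after launch is F − (r + 12), where F is the follow-up in weeks. In the pilot (about 26 weeks) that is 10, 6 or 2 weeks for r = 4, 8 or 12. The present endpoint already needs a start within 26 − 16 = 10 weeks for a week-16 weight. In the full study (about 104 weeks) the limits are 88, 84 and 80 weeks, so the endpoint is mainly informative there.
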